#### 2.2.1. Primary Endpoint Measures

Primary Endpoint / Cohort 1:

- Targeted safety and tolerability profile, inclusive of:
  - The incidence of AEs with causality related to VC-02 combination product, the surgical procedures required for VC-02 administration, and the immunosuppressive drug regimen.
  - The incidence of off-target growth as evidenced by implanted VC-02 units via lumen ultrasound measurements, or by histological examination of explants.
  - The incidence of immune sensitization defined by presence of donor anti-HLA antibodies absent prior to implant.

- Implant tolerability assessments (e.g., fever, erythema, pain, tenderness, induration) for up to four hours post-implantation and at subsequent visits.

Primary Endpoint / Cohort 2:

• Change from baseline to Week 26 in C-peptide AUC0-4h following an MMTT.

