## 5.2. Immunosuppression Medications

An immunosuppressive regimen will be prescribed for each subject to facilitate the engraftment and long-term function of implanted VC-02 units. The overall regimen may include the following agents (\**Day 1 is Implant Day*):

- Induction (Cohort 1)
  - Basiliximab: Recommended course of 20 mg IV on Day 1 and Day 5. However, it may be administered as early as Visit 2 (Week -4).
- Induction (Cohort 2)

If data collected from Cohort 1 indicate sufficient engraftment and cell viability is achieved with basiliximab, its use will continue in Cohort 2. However, if data from Cohort 1 and/or data collected in subsequent subjects in Cohort 2 indicate insufficient cell viability is achieved, the following agent may be utilized:

- Anti-thymocyte globulin (ATG) recommended course:
  - Day -2 (0.5 mg/kg IV) required dose
  - Day -1 (1.0 mg/kg IV) required dose
  - Day 1 (1.5 mg/kg IV) required dose
  - Up to two additional 1.5 mg/kg/day IV doses of ATG may be administered (on Day 2, and/or Day 3). Prior to any additional dose administration of ATG, an absolute lymphocyte count (ALC) will be obtained locally. If the ALC has been reduced by at least 90% versus the pre-ATG administration level, additional dose(s) of ATG may not be required. The Investigator should contact the Sponsor to determine the need for additional dosing.

However, ATG may be administered using the above dosing schedule as early as Visit 2 (Week -4).

• Maintenance (both Cohorts)

The starting doses and target serum trough concentration levels listed below are recommendations. As determined by the Investigator and after consultation with the Sponsor, the doses and target trough levels may be adjusted.

- Mycophenolate mofetil (MMF): Recommended starting dose of 1 gm PO BID as early as Visit 2 (Week -4). Adjust the dose downward for gastrointestinal side effects. Mycophenolic acid (Myfortic) may be taken alternatively to alleviate such side effects. Trough level measurements for MMF are not required.
- Tacrolimus:

- If combined with MMF: Recommended starting dose of 2 mg PO BID as early as Visit 2 (Week -4); target serum trough concentration level of 10-12 ng/mL during the first three (3) months. Adjust the dose to maintain a serum trough concentration level of 7-9 ng/mL thereafter. Serum creatinine values should also be collected in conjunction with Tacrolimus trough levels in order to monitor for potential renal toxicity.

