- If combined with sirolimus and MMF: Recommended starting dose of 0.1 mg/kg per day in two (2) equal divided doses to achieve a target serum concentration of 6-8 ng/mL.
- Sirolimus: Recommended starting dose of 0.1 mg/kg/day as early as Visit 2 (Week -4); target serum trough concentration level of 8-10 ng/mL by at least Week -2 prior to implantation. Post-implant, target serum trough concentration levels of 12-15 ng/mL for the three (3) months after implantation and serum trough concentration levels of 10-12 ng/mL thereafter plus MMF (2 g/day).

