# 6.2. Visit 2 / Screening (Week -4 to Week -2)

Subjects meeting eligibility criteria will return for Screening Visit 2 (Week -4). Subjects must be fasted for this visit. The following procedures will be completed:

- Review and confirm continued eligibility criteria.
- Obtain weight/vitals.
- Obtain all laboratory samples per the Schedule of Assessments.

*Note*: The immune panel blood samples may be collected at any time between Visit 2 and Visit 3, once the subject's study qualification is confirmed (Section 7.11.4).

• Perform the 4-hour MMTT. This is the baseline MMTT for efficacy evaluations.

- Dispense Continuous Glucose Monitoring (CGM) equipment and provide instructions. Insert the first sensor at the clinic. Confirm the CGM is functioning prior to the subject leaving the clinic.
- Dispense Self-Monitoring Blood Glucose (SMBG) equipment and provide instructions. Use of the meter provided by the Sponsor is required.
- Dispense the study diary and provide instructions. This is where the subject will capture insulin doses, details on HEs, and SMBG values. Remind the subject that eligibility for the trial requires daily compliance with entries between Visit 2 and 3.
- Dispense immunosuppression drugs and provide instructions for dosing (as needed).
- Assess AEs and concomitant medications.
- Contact the Sponsor to report any schedule changes or updates to the implant date.

The expected duration of the Screening Period is up to approximately five weeks. If the Enrollment Visit 3 is scheduled to occur beyond six weeks (>42 days) from the occurrence of Screening Visit 1, sites must contact the Sponsor before proceeding. Depending on the expected duration of the delay in conducting Visit 3, an Unscheduled Visit may be required to repeat certain screening procedures.

The overall Screening Period may be accelerated, but a minimum of two weeks must elapse between Visit 2 and Visit 3.

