## 4.6.3 Frequency of hypoglycemic events using subject-reported diary data

HE data collected on the "Hypoglycemic Event" eCRF page will be used collectively for HE data summary and analysis. These data are collected from the subject-completed diaries. Hypoglycemic event logs will be completed via subject diary (via provisioned phones) by subjects. Investigators will review the hypoglycemic event logs completed by the subjects at each study visit. Blank values in the hypoglycemic events (HEs) log are considered to be 0 values.

HEs will be classified in six ways: total HEs, severe HEs, nocturnal HEs, severe nocturnal HEs, daytime HEs, and severe daytime HEs. Total HEs are HEs that occur at any time during the 24-hour period. Severe HEs (SHEs) are HEs requiring the aid of another person to administer carbohydrates, glucagon, or other resuscitative assistance any time during the 24-hour period.

Nocturnal HEs are HEs that start during the 12 a.m. - 6 a.m. period. Severe nocturnal HEs are SHEs that start during the 12 a.m. - 6 a.m. period. Daytime HEs are HEs that start during the 6 a.m. to 12 a.m. period. Severe daytime HEs are SHEs that start during the 6 a.m. to 12 a.m. period.

The baseline average weekly frequency of subject-reported HEs, SHEs, nocturnal HEs, severe nocturnal HEs, daytime HEs and severe daytime HEs will be calculated using up to 28 days of data. The baseline average weekly frequency will be calculated using data starting at Day -3 (i.e., the day prior to immunosuppression induction) and working backwards for up to 28 days (through Day -30). For instances in which the available pre-implant dataset provides <28 days of data, the dataset will be supplemented with post-implant data, using data from Day 4 forward until 28 days of data is available. Data from days on which an MMTT or SOGCT was performed will not be used in the calculation.

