#### 72.1 Treatment-emergent Adverse Events

A treatment-emergent adverse event (TEAE) is defined as an AE that starts on or after the date of implant surgery.

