#### 72.7 Adverse Event Summaries

All AEs (serious and nonserious) occurring after completion of the informed consent process and before the end of study, regardless of relationship to study drug, will be included and classified by SOC and PT using MedDRA.

For TEAEs, the following will be summarized and presented for the SAS:

- i. An overall summary of TEAEs, which includes:
  - a. the number and percentage of subjects experiencing a TEAE
  - b. the number and percentage of subjects experiencing a TEAE by toxicity grade
  - c. the number and percentage of subjects experiencing a TEAE by relationship to VC-02 combination product
  - d. the number and percentage of subjects experiencing a TEAE by relationship to the surgical procedures required for VC-02 administration
  - e. the number and percentage of subjects experiencing a TEAE by relationship to the immunosuppressive drug regimen
  - f. the number and percentage of subjects experiencing a TEAE leading to study withdrawal
  - g. the number and percentage of subjects experiencing a treatment emergent SAE (TESAE)
  - h. the number and percentage of subjects experiencing a TESAE by toxicity grade
  - i. the number and percentage of subjects experiencing a TESAE by relationship to VC-02 combination product
  - j. the number and percentage of subjects experiencing a TESAE by relationship to the surgical procedures required for VC-02 administration
  - k. the number and percentage of subjects experiencing a TESAE by relationship to the immunosuppressive drug regimen
- ii. the number and percentage of subjects experiencing a TEAE by SOC and PT
- iii. the number and percentage of subjects experiencing a TEAE by SOC, PT and toxicity grade

- iv. the number and percentage of subjects experiencing a TEAE by SOC, PT and relationship to investigational product
- v. the number and percentage of subjects experiencing a TEAE by SOC, PT and relationship to the surgical procedures required for VC-02 administration
- vi. the number and percentage of subjects experiencing a TEAE by SOC, PT and relationship to immunosuppressive drug regimen.
- vii. the number and percentage of subjects experiencing a TEAE by SOC, PT and related to investigational product
- viii. the number and percentage of subjects experiencing a TEAE by SOC, PT and related to the surgical procedures required for VC-02 administration

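### Every AE table starts at implant surgery, but immunosuppression may start 2 to about 4 weeks earlier, so earlier regimen-related AEs are listed yet left out of the Cohort 1 primary incidence

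*SAP*

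**What the plan says.** **Endpoint.** Protocol 2.2.1 opens the Cohort 1 safety profile with "The incidence of AEs with causality related to VC-02 combination product" and, in the same item, extends it to the surgical procedures and the immunosuppressive regimen. SAP 2.2.1 repeats this. Neither limits the time of onset.

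**Window.** SAP 7.2.1: "A treatment-emergent adverse event (TEAE) is defined as an AE that starts on or after the date of implant surgery".

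**Tables.** SAP 7.2.7 introduces its outputs with "For TEAEs, the following will be summarized and presented for the SAS". There are 18 numbered summaries (i to xviii), and each counts TEAEs or treatment-emergent SAEs (TESAEs). The regimen appears in items i(e), i(k), vi, ix, xiv and xvii. Protocol 10.4.3 makes the same split: summaries use TEAEs, and listings hold all AEs.

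**Drug timing.** Protocol 5.2 recommends basiliximab, the Cohort 1 induction agent, on Day 1 and Day 5, then adds "However, it may be administered as early as Visit 2 (Week -4"). MMF, sirolimus, and tacrolimus given with MMF carry the same earliest start in both cohorts. For sirolimus the recommendation includes "target serum trough concentration level of 8-10 ng/mL by at least Week -2 prior to implantation". Protocol 6.2 has sites at Visit 2 "Dispense immunosuppression drugs and provide instructions for dosing (as needed").

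**The concern.** The TEAE window suits events attributed to the product or the operation, because exposure to both begins at surgery. The regimen is a third causal component, assessed separately (Protocol 8.1.1, SAP 7.2.3), and exposure to it can begin weeks earlier. For that component the tables start later than the exposure and are narrower than the endpoint.

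No other output fills the gap. SAP 7.6 covers off-target growth, immune sensitization and implant tolerability, and 7.6.3 draws only on AEs related to the product or the procedure. The SAP 7.2.7 tables are therefore the only incidence analysis of regimen-related AEs. At stake is a component of the Cohort 1 primary endpoint, which the plan as written can understate and cannot overstate by this route.

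**Working it through.** The plan gives no figure to reproduce, so the check sets the windows side by side and then sizes one affected subject.

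1. **Pre-surgery exposure**
   - Earliest start: Visit 2 (Protocol 5.2).
   - Shortest interval from Visit 2 to implantation: two weeks (Protocol 6.2).
   - Nominal interval: Week -4, target Day -29 (SAP 4.3), so about 4 weeks.
   - Range for a Visit 2 start: 2 to about 4 weeks.
   - Share of a full course with 104 weeks after implant: 2/(104 + 2) = 1.9% to 4/(104 + 4) = 3.7%.

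2. **ATG, Cohort 2 only and only if used**
   - On the default schedule the first dose is "Day -2 (0.5 mg/kg IV) required dose", followed by 1.0 mg/kg on Day -1 and 1.5 mg/kg on Day 1.
   - Required dose given before the surgery date: (0.5 + 1.0)/(0.5 + 1.0 + 1.5) = 1.5/3.0 = 50%.
   - With both optional 1.5 mg/kg doses: 1.5/6.0 = 25%.
   - Protocol 5.2 also allows the course from Visit 2, so all of it could precede surgery.

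3. **What happens to a pre-surgery event**
   - Recorded: yes, AEs are captured from Visit 2 (Protocol 8.1.5).
   - Coded in MedDRA: yes, from consent (SAP 7.2.7).
   - Listed with onset day, relationship to the regimen and a TEAE flag: yes (SAP 7.2.7).
   - Tabulated: no, in 0 of 18 summaries.
   - Two small exceptions: an AE on Day 1 before the operation is a TEAE, because the cut is by date. Some AEs with partial dates in the implant month are flagged treatment-emergent by rule (SAP 4.4).

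4. **Effect of one subject.** If a subject's only onset of a preferred term is before surgery, that term's rate is understated by 1/N:
   - N = 3 (Cohort 1 minimum): 33.3 percentage points
   - N = 15 (Cohort 1 maximum in Protocol 4.1): 6.7
   - N = 60 (Cohort 2 maximum): 1.7

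   SAP 4.2 counts VC02-102 subjects in Cohort 1, and the SAP revision table says three were enrolled. If they come on top of 15, N = 18 and the shift is 1/18 = 5.6 points. Rows by treatment group have smaller N and larger shifts.

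5. **Illustration with assumed counts.** The documents give no event rates. Intervals are 95% Clopper-Pearson.
   - One preferred term, N = 15: 2/15 = 13.3% (1.7 to 40.5). With one omitted subject restored, 3/15 = 20.0% (4.3 to 48.1). With three, 5/15 = 33.3% (11.8 to 61.6). With none, no change.
   - Any regimen-related AE, N = 15, one subject with a pre-surgery event: 10/15 = 66.7% (38.4 to 88.2) is unchanged if that subject also has a later regimen-related TEAE. It becomes 11/15 = 73.3% (44.9 to 92.2) if not.

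**The case against.** The strongest reply is that this is a disclosed choice with a fallback. Protocol 10.4.3 states the TEAE rule openly, the listing holds every event with its onset day and relationship, and in a cohort of 3 to 15 a reader could count the omitted events by hand. No hypothesis is tested, and the extra exposure is a few percent of two years. This limits the weight of the point. It does not remove it: the endpoint is an incidence, and a listing does not report one. The opening sentence of SAP 7.2.7 on all AEs after consent concerns inclusion and coding; no table for non-TEAEs follows it.

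A second reply is that Cohort 1 induction normally falls inside the window. This also stands in part. Basiliximab defaults to Day 1 and Day 5, and etanercept starts on Day 1. For Cohort 1 the gap rests on optional early basiliximab and on maintenance drugs whose doses and troughs are adjustable recommendations.

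Some stronger inferences are not supported:

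- *Pre-surgery AEs are lost.* They are recorded, coded and listed.
- *The SAP concedes that Cohort 1 induction precedes surgery, because its baselines run back from a point described as* "starting at Day -3 (i.e., the day prior to immunosuppression induction"). Those baselines serve efficacy analyses, which exclude Cohort 1 (SAP 4.2), and the day fits the Cohort 2 ATG schedule.
- *The ATG dose shares show harm to the primary endpoint.* ATG belongs to Cohort 2, whose primary endpoint is C-peptide. The shares bear only on the general AE tables.
- *Every sirolimus subject has at least two weeks of untabulated exposure.* The agent is optional and the target is a recommendation.

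**Conclusion.** The concern holds. In Safety Analysis Set subjects, regimen-related AEs with onset before the surgery date fall outside every planned incidence table, although the Cohort 1 primary endpoint includes them.

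The size cannot be computed from the documents and may be zero. Each affected subject moves a preferred term by 1/N: 6.7 points at N = 15, and 33.3 at the minimum of 3. The any-event figure moves only for a subject with no later regimen-related TEAE, so a reader should not infer that it must be understated.

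This rests on some Cohort 1 subjects starting immunosuppression before Day 1, which the protocol permits but does not require. The VC02-102 protocol is not among the documents, so the dosing of its subjects before surgery could not be checked in full. The gap is real and cheap to close, and should be closed. It does not undermine the safety analysis as a whole.

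**What to change.** Leave SAP 7.2.1 and items i to xviii unchanged. Add to SAP 7.2.7 a table, once for AEs and once for SAEs, with these features:

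- Population: the Safety Analysis Set.
- Events: AEs related to the immunosuppressive regimen, with onset from the first dose of protocol immunosuppression, or from surgery if that is earlier.
- Layout: by SOC and PT, by cohort and treatment group.
- Columns: onset before surgery, onset from surgery onward, and total.

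State that the total column is the regimen-related incidence for the Cohort 1 primary endpoint, and align Protocol 10.4.3.

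Widening the window inside the existing tables would be worse. A subject could then count in i(e) but not in i(a), a term in ix could exceed its count in ii, and the by-relationship items would admit unrelated pre-surgery AEs.

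Cost: one additional table set and no new data collection, since AE onset and relationship are recorded from Visit 2 and SAP 5.5 lists medication start dates. Regimen-related incidence may look slightly less favourable.

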#### 722 Adverse Event Toxicity Grade

The Investigator will use the National Cancer Institute Common Terminology Criteria for Adverse Event (NCI-CTCAE v4.0.3) guidelines to describe the maximum intensity of the AE. For purposes of consistency, these toxicity grades are defined as follows:

MILD	Asymptomatic, or mild symptoms, clinical or diagnostic observations noted; intervention not indicated.
MODERATE	Local or noninvasive intervention indicated.
SEVERE	Medically significant but not immediately life threatening, hospitalization or prolonged hospitalization.
LIFE-THREATENING	Life-threatening consequences, urgent intervention indicated.
DEATH	Death related to AE.

#### 723 Causality Assessment of Adverse Events

The Investigator's assessment of causality must be provided for all AEs (serious and nonserious). In relation to implantation with VC-02, there are three (3) main components to assessing causality. The Investigator's causality assessment must include a determination of whether there exists a reasonable possibility that:

- The investigational product (VC-02) itself caused or contributed to the AE.
- The surgical procedure (implantation or explanation) caused or contributed to the AE.
- The immunosuppression drug regimen caused or contributed to the AE.

In evaluating the causal relationship of an AE to VC-02, the surgical procedures, and the immunosuppression regimen, it is possible for the Investigator to determine causality as being associated to one or more of these factors. Conversely, the Investigator can determine that none of these relate to the AE.

Relationship of an AE to VC-02, the surgical procedures, and the immunosuppression drugs will be assessed as follows:

- Not related [unrelated or unlikely related]: A clinical event including laboratory test abnormalities without a temporal relationship to the investigational product exposure, the surgical procedures, or the immunosuppression drugs, which makes a causal relationship improbable, and/or in which other drugs, chemicals, or underlying disease provides plausible explanations.
- **Possibly related:** A clinical event, including laboratory test abnormality, with a reasonable time sequence to exposure of the investigational product or the surgical procedures, or the

immunosuppression drugs, but which could also be explained by concurrent disease or other drugs or chemicals.

• **Definitely related:** A clinical event, including laboratory test abnormality, occurring in a plausible time relationship to the investigational product exposure, surgical procedures, or the immunosuppression drugs, and which cannot be explained by concurrent disease or other drugs or chemicals.

The combined category of "related" AEs to investigational product exposure, surgical procedures, or the immunosuppression drugs, will include those events that are Unlikely Related, Possibly Related, Definitely Related.

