## 8.1.1. Causality Assessment of Adverse Events

The Investigator's assessment of causality must be provided for all AEs (serious and non-serious). In relation to implantation with VC-02, there are three (3) main components to assessing causality. The Investigator's causality assessment must include a determination of whether there exists a reasonable possibility that:

- The investigational product (VC-02) itself caused or contributed to the AE.
- The surgical procedure (implantation or explanation) caused or contributed to the AE.
- The immunosuppression drug regimen caused or contributed to the AE.

In evaluating the causal relationship of an AE to VC-02, the surgical procedures, and the immunosuppression regimen, it is possible for the Investigator to determine causality as being associated to one or more of these factors. Conversely, the Investigator can determine that none of these relate to the AE.

If the Investigator's final determination of causality is unknown, and the Investigator does not know if the investigational product, surgical procedure, or immunosuppression drugs caused the event, then the event will be classified as "related to investigational product" for reporting purposes. If the Investigator's causality assessment is "unknown but not related to investigational product", this should be clearly documented on study records.

Relationship of an AE to VC-02, the surgical procedures, and the immunosuppression drugs will be assessed as follows:

Not Related (Unrelated or Unlikely Related): A clinical event including laboratory test abnormalities without a temporal relationship to the investigational product exposure, the surgical

procedures, or the immunosuppression drugs, which makes a causal relationship improbable, and/or in which other drugs, chemicals, or underlying disease provides plausible explanations.

**Possibly Related:** A clinical event, including laboratory test abnormality, with a reasonable time sequence to exposure of the investigational product, the surgical procedures, or the immunosuppression drugs, but which could also be explained by concurrent disease or other drugs or chemicals.

**Definitely Related:** A clinical event, including laboratory test, occurring in a plausible time relationship to the investigational product exposure, surgical procedures, or the immunosuppression drugs, and which cannot be explained by concurrent disease or other drugs or chemicals.

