## 3. INVESTIGATIONAL PLAN

#### 3.1 Study Design

This Phase 1/2, first-in-human clinical trial is comprised of two study protocols: VC02-101 and VC02-102.

The VC02-101 study will be an open-label, FIH, clinical trial in subjects with T1DM and HU. Two cohorts are planned for enrollment in this trial, with enrollment of Cohort 1 occurring prior to enrollment of Cohort 2.

All VC02-101 enrolled subjects will have up to one or more VC-02-300 units and/or one or more smaller VC-02-20 (sentinel) units implanted in anatomical locations involving the trunk or extremities (e.g., back, flanks, arms, legs, and abdomen) suitable for implantation, as deemed appropriate by the Investigator and/or Surgeon after consultation with the Sponsor. Documentation of the implant plan for a subject will be provided to the Investigator by the Sponsor. Implantation will be executed under an anesthetic with or without sedation. The following are the maximum units that can be implanted per cohort:

- In Cohort 1, subjects are implanted with up to two (2) VC-02-300 units and up to six (6) sentinels; or up to ten (10) sentinels only.
- In Cohort 2, subjects are implanted with up to twelve (12) units. Of the twelve implanted units, no more than ten (10) will be VC-02-300 units, and the remainder will be VC-02-20 units. For example, if ten (10) VC-02-300 units are implanted, up to two (2) sentinels may also be implanted.

The VC02-102 study will be an open-label clinical trial in otherwise healthy subjects with T1DM. All subjects enrolled in Protocol VC02-102 are considered part of Cohort 1 for analysis purposes.

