## 72.4 Adverse Events of Special Interest (AESI)

Certain AEs may require additional investigation to ensure appropriate information and data are captured to appropriately evaluate the clinical development of VC-02. These are considered adverse events of special interest (AESI) and may include but are not limited to:

- AEs leading to the unexpected or premature explantation of VC-02-300 or sentinel units.
- AEs that result in early withdrawal from the study.
- Severe hypoglycemic events occurring after VC-02 implantation possibly or definitely related to VC-02.

If an AESI occurs, the Sponsor may request that additional data be collected for these events.

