- ix. the number and percentage of subjects experiencing a TEAE by SOC, PT and related to immunosuppressive drug regimen.
- x. the number and percentage of subjects experiencing a TESAE by SOC and PT
- xi. the number and percentage of subjects experiencing a TESAE by SOC, PT and toxicity grade
- xii. the number and percentage of subjects experiencing a TESAE by SOC, PT and relationship to investigational product
- xiii. the number and percentage of subjects experiencing a TESAE by SOC, PT and relationship to the surgical procedures required for VC-02 administration
- xiv. the number and percentage of subjects experiencing a TESAE by SOC, PT and relationship to immunosuppressive drug regimen.
- xv. the number and percentage of subjects experiencing a TESAE by SOC, PT and related to investigational product
- xvi. the number and percentage of subjects experiencing a TESAE by SOC, PT and related to the surgical procedures required for VC-02 administration
- xvii. the number and percentage of subjects experiencing a TESAE by SOC, PT and related to immunosuppressive drug regimen.
- xviii. the number and percentage of subjects experiencing a TEAE leading to study withdrawal by SOC and PT

In the overall summary of TEAEs table (i), besides tabulating the number and percentage of subjects, the total number of TEAE episodes will also be provided. If a subject has repeated episodes of a particular TEAE, all episodes will be counted in the summary table's total number of episodes.

In the remaining summary tables, the incidence of TEAEs will be calculated by dividing the number of subjects who have experienced the event by the total number of subjects in the SAS. Thus, the incidence of TEAEs is shown in terms of the total number of subjects and not in terms of the total number of episodes. If a subject has repeated episodes of a particular TEAE, only one episode per toxicity grade, or one episode per causal relationship, will be counted in the summary tables.

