#### 7.6.3 Implant Tolerability

The number and percentage of subjects enrolled in VC02-101 Cohort 1 experiencing implant tolerability assessments (e.g., fever, erythema, pain, tenderness, induration) for up to four hours post-implantation and at subsequent visits, will be summarized by cohort and treatment group. Implant tolerability assessments include AEs that are Possibly Related or Definitely Related to investigational product or to the surgical procedure.

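### SAP 7.2.3 classes unlikely-related events as not related, then counts them as related in the pooled tables that report a Cohort 1 primary endpoint component

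*SAP*

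**What the plan says.** Protocol 8.1.1 and SAP 7.2.3 both define three causality classes, applied separately to the product, the surgery and the immunosuppression. The lowest is "Not Related (Unrelated or Unlikely Related" in the protocol and "Not related [unrelated or unlikely related" in the SAP. Both describe it as the class in which a causal link is improbable. The other two classes are Possibly and Definitely Related. The protocol defines no pooled class.

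SAP 7.2.3 then adds one. Its last sentence says that the combined category of related AEs "will include those events that are Unlikely Related, Possibly Related, Definitely Related".

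SAP 7.2.7 uses that category in tables vii–ix for TEAEs and xv–xvii for TESAEs, one table per causality axis. Table vii, for example, gives "the number and percentage of subjects experiencing a TEAE by SOC, PT and related to investigational product". Tables iv–vi and xii–xiv show each relationship level separately.

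Two other SAP sections set a relatedness threshold for their own purposes, and both leave unlikely out:
- SAP 7.2.4 lists as an AESI "Severe hypoglycemic events occurring after VC-02 implantation possibly or definitely related to VC-02".
- SAP 7.6.3 says "Implant tolerability assessments include AEs that are Possibly Related or Definitely Related" to the product or the surgery.

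**The concern.** Within one SAP section, the same event is both not related and related. Both sentences are current text.

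This matters because protocol 2.2.1 and SAP 2.2.1 list the incidence of AEs related to the product, the surgery and the immunosuppression as the first component of the Cohort 1 primary endpoint. Tables vii–ix and xv–xvii report those three axes. A reader of a table headed related would not expect it to hold events whose causal link the plan itself calls improbable.

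Two components of that endpoint would also use different thresholds. A post-implant erythema rated unlikely would count as a related AE but would not count toward implant tolerability.

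**Working it through.** The plan states no figure to reproduce. The check is a comparison of text, followed by simple division to show what one subject is worth.

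**1. The rules side by side**

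| Place | Where an unlikely-related event falls |
|---|---|
| Protocol 8.1.1, class definition | Not related |
| SAP 7.2.3, class definition | Not related |
| SAP 7.2.3, combined category | Related |
| SAP 7.2.4, hypoglycemia AESI | Outside (Possibly or Definitely only) |
| SAP 7.6.3, implant tolerability | Outside (Possibly or Definitely only) |

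The third row contradicts the first two. The last two rows do not define related for the AE tables, so they show inconsistency of practice but do not add to the contradiction.

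**2. Is a reason given?** The SAP revision table says only that the combined category was clarified for the AE summaries. The protocol's one upward default (8.1.1) is for unknown causality, which is not the same as unlikely.

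**3. Effect, by what the eCRF records.** The documents do not show the eCRF options.
- *Unlikely is a separate level.* Pooling adds k subjects to the numerator on an axis, where k counts subjects whose only qualifying events on that axis are rated unlikely. The rise is k/N. It is never negative.
- *Only the three defined classes are recorded.* Unlikely cannot be separated from unrelated, so that term of the rule cannot be applied.

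**4. Size in the first case.** Inputs: Cohort 1 is at most 15 and the trial at most 75 (SAP 3.2.1). Three VC02-102 subjects were enrolled (SAP revision table), and SAP 3.1 states "All subjects enrolled in Protocol VC02-102 are considered part of Cohort 1 for analysis purposes". Whether they come on top of the 15 is not stated, so N = 18, 6 and 78 assume that they do. The values of k are assumed.

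| N | k = 1 | k = 3 |
|---|---|---|
| 15 | 1/15 = 6.7 points | 3/15 = 20.0 points |
| 18 (15 + 3) | 1/18 = 5.6 points | 3/18 = 16.7 points |
| 6 (minimum 3, + 3) | 1/6 = 16.7 points | – |
| 75 or 78 (overall safety set) | 1/75 = 1.3; 1/78 = 1.3 points | – |

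With k = 0 there is no effect. In treatment groups smaller than the cohort, each subject weighs more.

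**5. Can the by-level tables give the Possibly + Definitely incidence?** SAP 7.2.7 says that for repeated episodes "only one episode per toxicity grade, or one episode per causal relationship, will be counted in the summary tables". A subject with one possibly and one definitely related episode of the same event therefore appears in both rows. As an assumed example at N = 15, take 2 subjects in each row:
- complete overlap: max(2, 2)/15 = 2/15 = 13.3%
- no overlap: (2 + 2)/15 = 4/15 = 26.7%

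The rows alone do not say which value holds. Only the subject-level AE listing does.

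**The case against.** The strongest reply is that the numerical harm is conditional. The only scale the documents define has three classes. If those are the recorded levels, a programmer can read the sentence as an inclusion list in which unlikely matches no record. The tables then equal Possibly plus Definitely, and the defect is a stray word. That is a fair reading. It tempers any claim that the tables could not be produced, but the sentence would still need correcting.

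Other points on that side stand as limits:
- Protocol 10.4.3 asks for AEs by relationship. The by-level tables do this without the pooled category, so only six tables are affected.
- The AE listing gives relationship on all three axes, and a cohort of at most 15 can be counted by hand.
- The error can only overstate related events. It cannot hide a safety signal.
- SAP 3.2.1 caps Cohort 1 at 15 in total, so the figures at N = 18, 6 and 78 are less secure than those at N = 15.

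The suggestion that this is deliberate conservative pooling does not stand. Neither document says so, and deliberate pooling would still contradict the class definition and would need its own label.

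**Conclusion.** The concern holds. The contradiction lies wholly within SAP 7.2.3, and confidence in it is high; that confidence does not extend to the size of any effect. If unlikely is recorded separately, each subject with only unlikely events on an axis raises Cohort 1 related incidence by 6.7 percentage points at N = 15, and the number of such subjects is unknown. If it is not, the likely result is that the word has no effect.

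No hypothesis is tested, and the stopping rules, withdrawal criteria and AESI definition do not use the pooled category. The point should be fixed because it governs how a primary endpoint component is reported, but it does not threaten the conduct of the trial.

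**What to change.** Replace the last sentence of SAP 7.2.3 with: *The combined category of related events comprises Possibly Related and Definitely Related events only; Unrelated and Unlikely Related events are Not related.*

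Check whether the eCRF records unlikely as its own level, and list the recorded levels in SAP 7.2.3.

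If the sponsor wants a wider category, justify it and give it a distinct label, such as Unlikely, Possibly or Definitely Related. The minimum is one consistent, clearly labelled rule. Because the by-level rows cannot simply be added, I would also show the wider category only alongside the Possibly + Definitely incidence.

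The cost is one SAP sentence, one derivation and one check of the eCRF options. No new data are needed.
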